6.5.8.6.2 Missing Dates

All missing dates for medications or events that occur after randomization will be queried for a date. If no date is obtained, the following imputation rules will apply:

- For start dates, missing months and days will be imputed as "01", provided this occurs on or after the date of first study drug self-administration. Otherwise, the date or month (as appropriate) of the first self-administration of study drug will be used
- For stop dates, missing months will be imputed as "12" and missing days will be imputed as the last day of the month. If this creates a date after discontinuation/completion, the date of discontinuation/completion will be used

The imputed dates will only be used to classify events, medications, or therapy as treatment emergent or concomitant. Imputed dates will only be used in the table analyses. Listings will display the available date data.

6.5.8.6.3 Adverse Events

Whether the adverse event occurred after the first dose of study drug, relationship, and severity should not be missing and will be queried for value. If missing data is present, the AE date will be imputed as detailed above, will be assumed to be related to study drug, and will be assumed to be severe.

6.5.8.7 Interim Analyses and Data Monitoring

No interim analyses are planned for this trial.

6.5.8.8 Multicenter Studies

No formal by site analyses will be conducted. Analyses by sites for sites with a sufficient number of subjects can be conducted in an adhoc manner to confirm the uniformity of the overall results

6.5.8.9 Multiple Comparisons/Multiplicity

To control for inflation of type 1 error rate due to multiple hypotheses, the analysis of the two primary endpoints will be conducted in a hierarchical manner.

If both primary endpoints demonstrate statistically significant superiority of NOV03 versus saline at the two-sided alpha = 0.05 level, the following secondary endpoints will be tested hierarchically to maintain an overall two-sided alpha = 0.05.

- 1. CFB of Dryness Score (VAS) at Day 15
- 2. CFB in total Corneal Fluorescein Staining (tCFS) (NEI scale) at Day 15
- 3. CFB of VAS burning/stinging at Day 57
- 4. CFB in central cCFS (NEI scale) at Day 57

6.5.8.10 Use of an "Efficacy Subset" of Subjects

The primary analysis will be repeated in the PPS with observed data only as sensitivity analysis. Subjects in the PPS will be analyzed as treated.

6.5.8.11 Examination of Subgroups

If imbalances of interest are noted in the demographics and baseline characteristics, ad hoc summaries by subgroup can be produced.

6.5.9 Safety Analyses

All safety analyses will be performed on the SAF. The primary evaluation of safety of the active arm will be against the control arm.

6.5.9.1 Adverse Events

6.5.9.1.1 General Considerations for Analysis of Adverse Events

General considerations for AE summaries and calculations are:

- Multiple events by PT and SOC will be counted once per subject for each treatment
- For summaries by severity, the most severe event will be selected
- For summaries by relationship, the most related event will be selected

6.5.9.1.2 Adverse Event Dictionary

AEs will be coded using MedDRA version 22.1 or higher. Tables and listings will present data at the system organ class and preferred term level.

6.5.9.1.3 Treatment-Emergent Adverse Events

A treatment emergent adverse event (TEAE) is an AE that occurs or worsens after the first dose of trial treatment.

Where an AE is associated with a partially or fully missing start date or time, and it is unclear as to whether the AE is treatment emergent, it will be assumed that it is treatment emergent.

6.5.9.1.4 Adverse Event Severity

All AEs will be categorized as mild, moderate, or severe as directed in the study protocol.

6.5.9.1.5 Relationship of Adverse Events to Study Drug

All AEs will be categorized as related or not related as determined by investigator using these explanations as specified in the study protocol:

- Suspected: A reasonable possibility exists that the investigational product caused the AE
- Not Suspected: A reasonable possibility does not exist that the investigational product caused the AE

6.5.9.1.6 Serious Adverse Events

An AE is considered serious if, in the view of either the investigator, medical monitor or sponsor, it results in any of the following outcomes as specified in the protocol:

- Death
- A life-threatening AE
- Inpatient hospitalization or prolongation of existing hospitalization
- A persistent or significant incapacity or substantial disruption of the ability to conduct normal life functions
- A congenital anomaly/birth defect

Medically important

6.5.9.1.7 Summaries of Adverse Event

Treatment-emergent AEs will be summarized. Number of subjects or eyes experiencing a TEAE will be summarized by SOC and PT by treatment group and overall. In summary tables, SOC will be presented alphabetically and events within SOC will be presented by decreasing frequency count based on the total column.

Summary tables (number and percentage of subjects) of AEs will be provided by treatment as follows:

- All treatment-emergent AEs by SOC
- All treatment-emergent AEs by SOC and PT
- All treatment-emergent AEs by SOC, PT and maximal severity
- All treatment-emergent AEs by SOC, PT and strongest relationship
- All treatment-emergent AEs by SOC, PT, maximal severity, and strongest relationship
- All serious treatment-emergent AEs by SOC and PT
- All treatment-emergent AEs leading to premature discontinuation of treatment by SOC and PT
- All non-serious treatment-emergent AEs by SOC and PT occurring at the PT level at rates of 1%, 2%, 3%, 4%, and 5% in at least one treatment arm, separately by percentage

Separate summaries will be performed for ocular and non-ocular AEs. Ocular AEs will be summarized at the subject and eye levels, with separate eye level summaries for study and fellow eye.

An overview table will be provided summarizing the number of:

- TEAEs
- Serious TEAEs
- Serious TEAEs by reason for seriousness
- TEAEs leading to premature discontinuation of treatment
- TEAEs by worst severity
- TEAEs by worst relationship
- TEAEs by pattern
- TEAEs by outcome
- TEAEs by action taken
- TEAEs by action taken related to investigational product
- TEAE by expected or unexpected status

The treatment groups will be compared in regard to safety endpoints descriptively. No inferential comparison will be conducted.

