10.4.10 Safety Variables Analyses

All safety analyses will be performed on the Safety Population. The primary evaluation of safety of the active arm will be against the control arm.

Extent of Exposure

Dosing information for each treatment and each subject will be listed. Discontinuation of treatment will be summarized by treatment received. The primary reason for IMP discontinuation will also be summarized by treatment received.

Analysis of Adverse Events

Adverse events (AEs) will be coded using the MedDRA dictionary. Frequencies and percentages of subjects with TEAEs, serious TEAEs, and TEAEs causing premature discontinuation will be provided by treatment group. An AE is treatment emergent if it occurs or worsens after the first dose of trial treatment. Furthermore, frequencies will be

given of subjects with TEAEs by system organ class; by system organ class and preferred term; by system organ class, preferred term and maximal severity; by system organ class, preferred term and strongest relationship; and by system organ class, preferred term, maximal severity, and strongest relationship. Separate summaries will be performed for ocular and non-ocular AEs.

The treatment groups will be compared in regard to safety endpoints descriptively. No inferential comparison will be conducted.

Concomitant Medications

Concomitant medications will be coded using the most recent version of WHO-Drug Dictionary and summarized by treatment group.

Other safety endpoints including those assessed by visual acuity, slit-lamp biomicroscopy, dilated fundoscopy, and intraocular pressure will be summarized by treatment group and visit using descriptive statistics. Changes from baseline will also be summarized where appropriate. For assessments performed by eye, study eye and fellow eye will be summarized separately.

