- Summary of Fellow Eye CFS by Sub-region (NEI scale) FAS 14.2.8.2
- Analysis of Proportion of Study Eye tCFS Responders FAS 14.2.9.1
- 14.2.9.2 Analysis of Proportion of Fellow Eye tCFS Responders – FAS
- 14.2.9.3 Sensitivity Analysis of Proportion of Study Eye tCFS Responders – FAS
- 14.2.9.4 Sensitivity Analysis of Proportion of Fellow Eye tCFS Responders – FAS
- 14.2.10.1 Analysis of Proportion of Dryness Score Responders FAS
- 14.2.10.2 Sensitivity Analysis of Proportion of Dryness Score Responders FAS
- 14.2.11.1 Analysis of VAS FAS
- 14.2.11.2 Sensitivity Analysis of VAS FAS
- 14.2.12.1 Analysis of Ocular Surface Disease Index Score FAS
- 14.2.12.2 Sensitivity Analysis of Ocular Surface Disease Index Score FAS
- 14.2.13 Summary of Individual Ocular Surface Disease Index Questionnaire Items – **FAS**
- 14.2.14.1 Analysis of Study Eye Total Meibomian Gland Score (MGD score) FAS
- 14.2.14.2 Analysis of Fellow Eye Total Meibomian Gland Score (MGD score) FAS
- Summary of Individual Study Eye Meibomian Gland Results FAS 14.2.15.1
- 14.2.15.2 Summary of Individual Fellow Eye Meibomian Gland Results FAS
- Overview of Study Eye Ocular Adverse Events SAF 14.3.1.1
- 14.3.1.2 Overview of Fellow Eye Ocular Adverse Events – SAF
- 14.3.1.3 Subject Level Overview of Ocular Adverse Events – SAF
- Overview of Non-ocular Adverse Events SAF 14.3.1.4
- 14.3.2.1 Study Eye Ocular Treatment Emergent Adverse Events by SOC – SAF
- 14.3.2.2 Fellow Eye Ocular Treatment Emergent Adverse Events by SOC – SAF
- Non-ocular Treatment Emergent Adverse Events by SOC SAF 14.3.2.3
- 14.3.3.1 Study Eye Ocular Treatment Emergent Adverse Events by SOC and PT – SAF
- 14.3.3.2 Fellow Eye Ocular Treatment Emergent Adverse Events by SOC and PT – SAF
- 14.3.3.3 Non-ocular Treatment Emergent Adverse Events by SOC and PT – SAF

- 14.3.4.1 Study Eye Ocular Treatment Emergent Adverse Events by SOC, PT, and Maximal Severity SAF
- 14.3.4.2 Fellow Eye Ocular Treatment Emergent Adverse Events by SOC, PT, and Maximal Severity SAF
- 14.3.4.3 Non-ocular Treatment Emergent Adverse Events by SOC, PT, and Maximal Severity SAF
- 14.3.5.1 Study Eye Ocular Treatment Emergent Adverse Events by SOC, PT, and Strongest Relationship SAF
- 14.3.5.2 Fellow Eye Ocular Treatment Emergent Adverse Events by SOC, PT, and Strongest Relationship SAF
- 14.3.5.3 Non-ocular Treatment Emergent Adverse Events by SOC, PT, and Strongest Relationship SAF

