- 14.3.6.1 Study Eye Ocular Treatment Emergent Adverse Events by SOC, PT, Maximal Severity, and Strongest Relationship SAF
- 14.3.6.2 Fellow Eye Ocular Treatment Emergent Adverse Events by SOC, PT, Maximal Severity, and Strongest Relationship SAF
- 14.3.6.3 Non-ocular Treatment Emergent Adverse Events by SOC, PT, Maximal Severity, and Strongest Relationship SAF
- 14.3.7.1 Study Eye Ocular Serious Treatment Emergent Adverse Events by SOC and PT SAF
- 14.3.7.2 Fellow Eye Ocular Serious Treatment Emergent Adverse Events by SOC and PT SAF
- 14.3.7.3 Non-ocular Serious Treatment Emergent Adverse Events by SOC and PT SAF
- 14.3.8.1 Study Eye Ocular Treatment Emergent Adverse Events Leading to Premature Discontinuation of Treatment by SOC and PT SAF
- 14.3.8.2 Fellow Eye Ocular Treatment Emergent Adverse Events Leading to Premature Discontinuation of Treatment by SOC and PT SAF
- 14.3.8.3 Non-ocular Treatment Emergent Adverse Events Leading to Premature Discontinuation of Treatment by SOC and PT SAF
- 14.3.9.1 Study Eye Ocular Non-serious Treatment Emergent Adverse Events by SOC and PT Occurring at the PT Level at Rates of 1%, 2%, 3%, 4%, and 5% in at Least one Treatment Arm SAF
- 14.3.9.2 Fellow Eye Ocular Non-serious Treatment Emergent Adverse Events by SOC and PT Occurring at the PT Level at Rates of 1%, 2%, 3%, 4%, and 5% in at Least one Treatment Arm SAF
- 14.3.9.3 Non-ocular Non-serious Treatment Emergent Adverse Events by SOC and PT Occurring at the PT Level at Rates of 1%, 2%, 3%, 4%, and 5% in at Least one Treatment Arm SAF
- 14.4.1.1 Summary of Study Eye BCVA (logMAR) Results and Change from Baseline by Visit SAF
- 14.4.1.2 Summary of Fellow Eye BCVA (logMAR) Results and Change from Baseline by Visit SAF
- 14.4.2.1 Summary of Study Eye Slit-lamp Biomicroscopy Results by Location and Visit SAF

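### The SAP's table index lists ocular TEAEs by SOC and preferred term per eye only, although its text promises them at subject level as well

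*SAP*

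**What the plan says.** **The text promises subject counts.** Protocol 10.4.10: "Frequencies and percentages of subjects with TEAEs, serious TEAEs, and TEAEs causing premature discontinuation will be provided by treatment" group. It extends this to breakdowns by SOC, preferred term, severity and relationship, with ocular and non-ocular events separated. SAP 6.5.9.1.7 introduces its list of AE tables with "Summary tables (number and percentage of subjects) of AEs will be provided by treatment as follows", and adds for ocular events: "Ocular AEs will be summarized at the subject and eye levels, with separate eye level summaries for study and fellow eye". The counting rule in SAP 6.5.9.1.1 is also per subject: "Multiple events by PT and SOC will be counted once per subject for each treatment". One sentence in 6.5.9.1.7 leaves the unit open: "Number of subjects or eyes experiencing a TEAE will be summarized by SOC and PT by treatment group and overall".

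**The index plans eye counts.** In SAP section 7, table 14.3.1.3 is "Subject Level Overview of Ocular Adverse Events". No other ocular AE table is titled as subject level. Series 14.3.2 to 14.3.9 follow one pattern, for example 14.3.3.1, "Study Eye Ocular Treatment Emergent Adverse Events by SOC and PT", then the fellow-eye version at .2 and the non-ocular version at .3. The frequency series 14.3.9, whose titles contain "Occurring at the PT Level at Rates of 1%, 2%, 3%, 4%, and 5% in at Least one" treatment arm, is built in the same way.

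**The concern.** Both eyes are dosed, so a subject can have a given event in one eye or in both. The usual safety figure, and the one both documents promise, is the percentage of subjects per arm with each preferred term. Tables programmed from the index would not contain that figure for ocular events. It also cannot be worked out from the two eye tables, because they do not show how many subjects appear in both.

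The frequency tables have a related problem. A cut-off applied to one eye at a time uses a count that can be lower than the subject count and never higher. Any error therefore runs towards leaving a term out of a frequency table. Ocular AE incidence in the earlier NVU-002 trial was 4.5% to 11.7% over all ocular events (protocol 2.4), so single terms may well lie in the 1% to 5% range where the cut-offs operate.

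**Working it through.** **Step 1: count the indexed tables.** Series 14.3.2 to 14.3.9 are 8 series of 3 tables, 24 in all: 16 ocular by eye, 8 non-ocular, and no subject-level ocular table. No table combining ocular and non-ocular TEAEs is indexed either. The overview 14.3.1.3 has, by the content listed in 6.5.9.1.7, no SOC or preferred-term rows.

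**Step 2: is a table merely hidden?** Series 14.3.1 runs study eye, fellow eye, subject level, non-ocular. In the other series non-ocular follows directly at .3. A removed subject-level table in that order would leave a gap in the numbering, and there is none.

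**Step 3: is this the index's convention?** No. Ocular medical history and ocular concomitant medications each have study-eye, fellow-eye and subject-level tables in the same index.

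**Step 4: what the eye tables say about subjects.** Input: 280 subjects per arm (SAP 6.5.10), taken as 280 study eyes and 280 fellow eyes. If A subjects have the term in the study eye and F in the fellow eye, then

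subjects = A + F − (subjects with both eyes affected).

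The overlap lies between 0 and the smaller of A and F, so the subject count lies between max(A, F) and A + F.

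| Study eye | Fellow eye | Subjects, minimum | Subjects, maximum |
|---|---|---|---|
| 7 | 7 | 7 (2.5%) | 14 (5.0%) |
| 10 | 8 | 10 (3.6%) | 18 (6.4%) |
| 13 | 13 | 13 (4.6%) | 26 (9.3%) |

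**Step 5: effect on the cut-offs.** Reading each cut-off as *at least*, which the SAP does not state, 1%, 2%, 3%, 4% and 5% of 280 are 2.8, 5.6, 8.4, 11.2 and 14, so 3, 6, 9, 12 and 14 are needed. The bilateral share b is not in the documents; take it from 0 to 1. With unilateral events split evenly between eyes, S affected subjects give an expected count in each eye table of

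S × [b + (1 − b)/2].

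For S = 14, which is 5.0% of subjects:

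| b | Expected count per eye table | Per-eye rate | Share of subject count |
|---|---|---|---|
| 0 | 7.0 | 2.5% | 50% |
| 0.5 | 10.5 | 3.75% | 75% |
| 0.9 | 13.3 | 4.75% | 95% |
| 1 | 14.0 | 5.0% | 100% |

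Two boundary cases. Four unilateral cases split 2 and 2 are 4/280 = 1.4% of subjects but 2/280 = 0.7% in each eye table, below the 1% cut-off. Twenty-six unilateral cases split 13 and 13 are 9.3% of subjects but 4.6% per eye, below the 5% cut-off.

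**The case against.** The best defence is that the text governs. SAP 6.5.9.1.7 commits to the subject level in plain terms, and an index that leaves out some titles does not cancel that. The index may simply be incomplete. This stands as far as it goes, but tables are usually programmed from the index, and the remedy for an incomplete index is to complete it.

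Three stronger readings are tempting, and the documents do not support them.

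- *The cut-offs are applied to half-counts.* Halving needs every event to be unilateral and the cases to split evenly. A bilateral event appears in full in both eye tables, and no bilateral share is given.
- *Subject counts will not be available.* The overview gives subject-level ocular totals, and listings 16.2.7.1 to 16.2.7.3 (all AEs, those leading to discontinuation, serious AEs) allow a count by hand. The gap is in the planned summary tables.
- *Terms will vanish from the report.* Series 14.3.9 covers non-serious events only, and tables 14.3.3.1 and 14.3.3.2 list every term without a cut-off.

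The boundary cases are also chosen splits. If laterality is random (an assumption), 26 unilateral cases miss the 5% cut-off in both eye tables only at exactly 13 and 13, with probability C(26,13)/2^26 = 15.5%. Four miss the 1% cut-off only at 2 and 2, with probability 6/16 = 37.5%. Bilateral cases lower these figures, and a term missed in one arm may still qualify through the other. A term at 4.6% per eye also still meets the 1% to 4% cut-offs. Finally, safety comparisons are descriptive, with no inferential test.

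**Conclusion.** The inconsistency is real and minor. Protocol 10.4.10 and SAP 6.5.9.1.7 promise subject incidence for ocular TEAEs by SOC and preferred term. The index plans it per eye only, and SAP 6.6 records no change from the planned analyses. As indexed, the number of subjects with an ocular term is known only to lie between the larger eye count and the sum of the two, a range of up to a factor of two. Per-eye rates in 14.3.9 fall short of subject rates by between nothing and about half.

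This rests on three assumptions: about 280 treated subjects per arm, each contributing one study eye and one fellow eye; cut-offs meaning *at least*; and cut-offs acting on the unit named in each table's title. The size within the range depends on the bilateral share, which the documents do not give. No data collection, type I error or primary conclusion is affected.

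**What to change.** - Add a subject-level ocular table to each of series 14.3.2 to 14.3.9, placed before the non-ocular table as in 14.3.1. Count a subject once per preferred term if either eye is affected.
- Apply the 1% to 5% cut-offs of 14.3.9 to subject percentages, and say in 6.5.9.1.7 that the unit is the subject and whether a cut-off means *at least*.
- Keep the eye-level tables as supportive.

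The cost is about eight extra tables from the existing dataset and an update to the index before database lock. No new data are needed.

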6.5.9.2 Safety Laboratory Values

Safety laboratory tests will not be collected. Urine pregnancy test results will be captured at Visit 0, Visit 1, and Visit 4. Urine pregnancy test results will be included in a listing.

6.5.9.3 Vital Sign Measurements

Vital signs data will not be collected.

6.5.9.4 Other Safety Measurements

Visual acuity, slit-lamp biomicroscopy, dilated fundoscopy, and intraocular pressure will be summarized by treatment group and visit using descriptive statistics in SAF. Changes from baseline will also be summarized where appropriate. For assessments performed by eye, study eye and fellow eye will be summarized separately.

6.5.9.4.1 Visual Acuity

Visual acuity will be performed at screening, Visits 1-4, and early termination. The base logMAR, which is the last line in which a letter is read correctly, and the number of total letter missed up to and including the last line read will be collected on the CRF. The calculated logMAR will be automatically generated by the EDC as base logMAR + (number of total letters missed × 0.02). Descriptive statistics for the calculated LogMAR Score will be presented for study eye and fellow eye by treatment and overall at baseline and all post-baseline visits in the SAF. Changes from baseline will also be summarized.

6.5.9.4.2 Slit-lamp Biomicroscopy

Biomicroscopy will be performed at screening, Visits 1-4, and early termination. Observations will be graded as Normal, Abnormal Clinically Significant, or Abnormal Not Clinically Significant. Lids, cornea, conjunctiva, anterior chamber, iris and lens will be examined. If 'Check if no changes since Visit 0' is checked, the results of the tests at Visit 0 will be used for analysis at that timepoint. Listings will display 'No changes since Visit 0'. Descriptive statistics for the grading by each domain will be presented for study eye and fellow eye by treatment and overall at baseline and all post-baseline visits in the SAF. Shifts from baseline indicative of worsening will also be summarized. Worsening is defined as a shift from normal to abnormal not clinically significant, normal to abnormal clinically significant.

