5.4 Exclusion Criteria

Subjects will not be eligible to participate in this trial **if any** of the following criteria apply:

1. Have been randomized in NVU-002, NVU-003 or participated in the NVU-004 OLE Study.
2. Have any clinically significant ocular surface slit-lamp findings at Visit 0 and Visit 1 and/or in the opinion of the investigator have any findings that may interfere with trial parameters and may include eye trauma, history of eye trauma or anterior membrane dystrophy.
3. Have a history of Stevens Johnson Syndrome.
4. Have active blepharitis or lid margin inflammation that required any topical antibiotics or topical steroids within last 30 days prior to Visit 0 or will require such treatment during the trial. Any other lid margin therapy such as lid scrubs, lid wipes, warm compresses, systemic antibiotics (such as tetracyclines) and oral supplements for treatment of ocular conditions or oral supplements had to be stable within the last 30 days prior to Visit 1 and should be maintained stable throughout the trial.
5. Have had a LipiFlow procedure, Intense Pulse Light (IPL) procedure or any kind of other procedures affecting meibomian glands within 6 months prior to Visit 1.
6. Have abnormal lid anatomy that causes incomplete eyelid closure including entropion and ectropion or floppy lid syndrome that exposes parts of the conjunctiva or impairs the blinking function of the eye (e.g. Botox injections for blepharospasm).
7. Have received or removed a permanent punctum plug within 3 months (6 months for dissolvable punctum plugs) prior to Visit 1 or expected to receive a punctum plug or removal of a punctum plug, or a punctum plug expected to be dissolved during the trial.
8. Have Dry Eye Disease secondary to scarring, irradiation, alkali burns, cicatricial pemphigoid, or destruction of conjunctival goblet cells (as with vitamin A deficiency).
9. Have an ocular or periocular malignancy.
10. Have a corneal epithelial defect; have significant confluent staining or filaments anywhere on the cornea.
11. Have a history of herpetic keratitis.
12. Have active ocular allergies or ocular allergies that are expected to be active during the trial period.
13. Be diagnosed with an active ocular or systemic infection (bacterial, viral, or fungal), including fever requiring treatment with antibiotics.

14. Have worn contact lenses within 1 month of Visit 0 or anticipate using contact lenses during the trial.

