9 ADVERSE EVENTS

9.1 Adverse Event

An adverse event (AE) is defined as any untoward medical occurrence associated with the use of a drug in humans, whether or not the event is considered drug-related. An AE can therefore be any unfavorable and unintended sign (e.g., an abnormal laboratory finding), symptom, or disease occurring after the subject signature of the ICF without any judgment on causality.

If there is a worsening of a medical condition that was present prior to Visit 0, this should also be considered a new AE and reported. Any medical condition present prior to the administration of the IMP that remains unchanged or improved should not be recorded as an AE at subsequent visits.

Worsening of DED will be considered an AE only if the dry eye status of the subject exceeds their previous experiences with the condition. This will be determined by the subject and the investigator.

A clinically significant visual acuity worsening (defined as an increase of 0.22 or greater in logMAR score) from screening (Visit 0) will be considered an Adverse Event.

Documentation regarding the AE should be made as to the nature, date of onset, end date, severity, relationship to IMP, expectedness, action(s) taken, seriousness, and outcome of any sign or symptom observed by the physician or reported by the subject upon non-leading AE questioning.

AEs (both elicited and observed) and SAEs will be monitored throughout the trial. The investigator will promptly review all AEs for accuracy and completeness. All AEs will be documented on the appropriate source document and eCRF.

Adverse events recorded from the signing of informed consent through the last study visit must be reported, regardless of whether or not the AEs are considered study-related.

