6.5.9.4.3 Dilated Fundoscopy Examination

A dilated fundoscopy examination will be performed during the trial at screening, Visit 4 and early termination. Observations will be graded as Normal, Abnormal CS or Abnormal NCS. Vitreous, retina, macula, choroid and optic nerve will be examined. If 'Check if no changes since Visit 0' is checked, the results of the tests at Visit 0 will be used for analysis at that timepoint. Listings will display 'No changes since Visit 0'. Descriptive statistics for the grading by each domain will be presented for study eye and fellow eye by treatment and overall at baseline and all post-baseline visits in the SAF. Shifts from baseline indicative of worsening will also be summarized. Worsening is defined as a shift from normal to abnormal

not clinically significant, normal to abnormal clinically significant, and abnormal not clinically significant to abnormal clinically significant.

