14422 Summary of Fellow Eye Slit-lamp Biomicroscopy Results by Location and Visit – SAF Worsening Shifts in Study Eye Slit-lamp Biomicroscopy Results—SAF 14.4.3.1 Worsening Shifts in Fellow Eye Slit-lamp Biomicroscopy Results—SAF 14.4.3.2 Summary of Study Eve Dilated Fundoscopy Results by Location and Visit – 14.4.4.1 **SAF** 14442 Summary of Fellow Eye Dilated Fundoscopy Results by Location and Visit – SAF 14.4.5.1 Worsening Shifts in Study Eye Dilated Fundoscopy Results–SAF Worsening Shifts in Fellow Eye Dilated Fundoscopy Results-SAF 14.4.5.2 Summary of Study Eye Intraocular Pressure and Change from Baseline by Visit 14.4.6.1 - SAF Summary of Fellow Eye Intraocular Pressure and Change from Baseline by 14.4.6.2 Visit – SAF Listings 16.2.1 **Subject Disposition** 16.2.2.1 **Inclusion Criterion** 16.2.2.2 **Exclusion Criterion** 16.2.2.4 **Protocol Deviations** 16.2.3.1 Subjects Excluded from the Per Protocol Analysis Set 16.2.4.1 Demographic and Baseline Information 16.2.4.2 Ocular Medical History Ocular Surgical History 16.2.4.3 16.2.4.4 Non-ocular Medical History 16.2.4.5 Non-ocular Surgical History Dosing Compliance and Exposure 16.2.5.1 16.2.5.2 Dispense Investigational Drug Daily Dosing Diary 16.2.5.3 Randomized and Actual Treatments 16.2.5.4 16.2.6.1 Corneal Fluorescein Staining (CFS) by Area and Total Score 16262 Dryness Score (VAS) Ocular Symptoms (VAS) 16.2.6.3 16.2.6.4 Ocular Surface Disease Index (OSDI) 16.2.6.5 Meibomian Gland Assessment (MGD Score) 16.2.6.6 Schirmer's Test I (Without Anesthesia) Tear Film Break-up Time (TFBUT) 16.2.6.7 16.2.6.8 **Instillation Comfort Questionnaire** 16.2.6.9 **Evedrop Acceptability Questionnaire** Collection of Returned Investigational Product 16.2.6.10 All Adverse Events by SOC, PT, and Verbatim Term 16.2.7.1 Adverse Events Leading to Premature Discontinuation of Treatment 16.2.7.2 Serious Adverse Events 16.2.7.3 16.2.7.4 **Subject Deaths Pregnancy Test** 16.2.8.1 Visual Acuity 16.2.9.1

Protocol Number: 904

6.2.9.2	Slit-lamp Biomicroscopy
6.2.9.3	Dilated Fundoscopy
6.2.9.4	Intraocular Pressure
6.2.9.5	Ocular Concomitant Medications
6.2.9.6	Ocular Concomitant Therapies
6.2.9.7	Non-ocular Concomitant Medications
6.2.9.8	Non-ocular Concomitant Therapies
6.3.1	Unscheduled Visits
6.3.2	Subject Completion

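### The SAP's slit-lamp worsening definition leaves out the shift from abnormal not clinically significant to abnormal clinically significant, which its fundoscopy definition counts on the same three grades

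*SAP*

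**What the plan says.** SAP 6.5.9.4.2 sets a three-level scale for slit-lamp biomicroscopy: "Observations will be graded as Normal, Abnormal Clinically Significant, or Abnormal Not Clinically Significant". It plans a summary of shifts from baseline that indicate worsening, and defines them as follows: "Worsening is defined as a shift from normal to abnormal not clinically significant, normal to abnormal clinically significant". The sentence stops there.

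SAP 6.5.9.4.3 uses the same three grades for dilated fundoscopy. Its definition of worsening starts in the same way but goes on to a third shift: "not clinically significant, normal to abnormal clinically significant, and abnormal not clinically significant to abnormal clinically significant".

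The slit-lamp definition feeds Table 14.4.3.1, listed in SAP section 7 as "Worsening Shifts in Study Eye Slit-lamp Biomicroscopy Results", and its fellow-eye counterpart, Table 14.4.3.2. Slit-lamp biomicroscopy is a named safety endpoint in Protocol 6.2 and a safety variable in SAP 6.4.2. Protocol 10.4.10 asks for descriptive summaries and, where appropriate, changes from baseline. It gives no definition of worsening of its own.

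**The concern.** The two definitions should agree, because they apply the same ordered scale to the same kind of observation, and the SAP gives no reason for treating them differently. Under the slit-lamp rule, an eye whose cornea or lids are graded NCS at baseline and CS later is not a worsening. Under the fundoscopy rule, the same change in the retina or macula is.

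The omitted shift could occur in this population. Exclusion criterion 2 in Protocol 5.4 bars subjects who "Have any clinically significant ocular surface slit-lamp findings at Visit 0 and Visit 1", but does not bar NCS findings as such. Ocular surface structures should therefore enter as Normal or NCS. Every subject must also have meibomian gland dysfunction and corneal staining in a qualifying eye (Protocol 5.3). NCS grades for lids or cornea at baseline are therefore plausible, although neither document gives a baseline distribution.

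At stake is whether the two slit-lamp shift tables are complete. A reader comparing them with the fundoscopy shift tables would reasonably assume that both count every deterioration.

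**Working it through.** The plan states no figure on this point, so there is none to reproduce. The check is a full list of the possible shifts, compared with each definition.

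**Inputs**
- Scale: Normal < NCS < CS (SAP 6.5.9.4.2 and 6.5.9.4.3; SAP 6.5.4.1.5 uses the same grades at baseline).
- Slit-lamp worsening: two shifts (SAP 6.5.9.4.2).
- Fundoscopy worsening: three shifts (SAP 6.5.9.4.3).
- Planned size: 280 subjects per arm, one study eye each (Protocol 10.3 and 10.4.2).

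**Step 1: list the worsening shifts.** Three ordered grades give 3 × 2 / 2 = 3 upward shifts.

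| Shift | Slit-lamp rule | Fundoscopy rule |
|---|---|---|
| Normal to NCS | counted | counted |
| Normal to CS | counted | counted |
| NCS to CS | **not counted** | counted |
| Total | 2 of 3 | 3 of 3 |

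**Step 2: split the slit-lamp rule by baseline grade.**
- Baseline Normal: 2 of 2 possible worsening shifts are counted.
- Baseline NCS: 0 of 1 is counted. NCS to CS is the only way such a structure can worsen.
- Baseline CS: no higher grade exists, so neither rule can record a worsening.

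The loss therefore falls entirely on structures that are NCS at baseline.

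**Step 3: convert to eyes.** Let *s* be the share of study eyes graded NCS at baseline for one structure. The number per arm that cannot count as worsened in Table 14.4.3.1 is 280 × *s*. The documents do not give *s*, so it has to be treated as an assumption:
- each 10 percentage points: 280 × 0.10 = 28 eyes per arm;
- full range: 280 × 0 = 0 to 280 × 1 = 280 eyes per arm.

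These are eyes for which the table could not register a worsening. They are not an estimate of worsenings missed. That number is 280 × *s* × (probability of moving from NCS to CS), and the documents give neither *s* nor the probability. The tables also use the Safety Set, that is, subjects who were dosed, so 280 is a planning figure.

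**The case against.** The strongest reply is that this is a dropped phrase with little practical effect. The slit-lamp sentence joins its two items with a comma and no conjunction, and otherwise runs parallel to the fundoscopy sentence. That suggests lost words and not a decision to ignore the shift. This is fair, and the sentence should be checked against the source SAP. But it ends in a full stop with no sign of a redaction or gap, and a programmer following it would leave the category out.

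The second part of the reply is that the information survives elsewhere:
- Table 14.4.2.1 ("Summary of Study Eye Slit-lamp Biomicroscopy Results by Location and Visit") and Table 14.4.2.2 show the grades at every visit, and Listing 16.2.9.2 shows them by subject.
- Under Protocol 9.1, worsening of a condition present before Visit 0 "should also be considered a new AE and reported". The same section limits this for dry eye disease itself.
- Because exclusion 2 should keep CS findings off the ocular surface at entry, a later CS grade there already implies deterioration. If the shift tables are laid out by visit, which the SAP does not say, subtracting the Normal to CS count from the total CS count would largely recover the missing category.
- On safety endpoints the SAP says "No inferential comparison will be conducted".

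Most of this stands, and it is why the point is minor. It does not make the definition right. The by-visit tables do not link an eye's later grade to its baseline grade. The subtraction does not carry over to the anterior chamber, iris and lens, because exclusion 2 is worded for ocular surface findings. The listing would have to be counted by hand.

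The last part of the reply is that the eye counts could be mistaken for affected eyes. That is a fair caution, and the firm result is 2 of 3 shifts against 3 of 3.

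**Conclusion.** The concern holds, as a minor point. Followed exactly, SAP 6.5.9.4.2 would make Tables 14.4.3.1 and 14.4.3.2 report a real NCS to CS deterioration as no worsening, while the fundoscopy shift tables would count the same change. The effect is confined to those two descriptive tables. Efficacy results, power, type I error and the other planned safety outputs do not change.

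The conclusion rests on two assumptions: that the sentence in the source SAP reads as it does here, and that the three grades are ordered Normal, NCS, CS, which the fundoscopy definition itself implies. The number of events affected cannot be determined from the documents and may be small.

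**What to change.** First, confirm in the source SAP that the sentence is complete as shown. If it is, add the shift from NCS to CS to the definition in 6.5.9.4.2, taking the wording from the end of the definition in 6.5.9.4.3, and program it as a third category in Tables 14.4.3.1 and 14.4.3.2. Make the change as a documented SAP amendment before database lock and unmasking, as SAP section 4 provides.

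The cost is one phrase in the SAP and one extra shift category in two tables. The grades are already collected at the required visits, so no new data are needed.
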